6.6 Subject compliance

Throughout the trial, the Investigator will remind the Subjects to follow the trial procedures and requirements to ensure Subject compliance. If a Subject is found to be non-compliant, the Investigator will remind the Subject of the importance of following the instructions given including taking the trial products as prescribed.

Treatment compliance: To ensure treatment compliance, the Investigator will at each visit assess the Subject's compliance by evaluating the drug accountability, glycemic control, amount of time in auto mode, adherence to the visit schedule, completion of the Subject's diary, and the SMPG values in the CareLink Clinical Report. If a Subject is being non-compliant with the treatment, then the Investigator must discuss this with the Subject and emphasize the importance of being in compliance.

7 Trial supplies

Trial supplies comprise trial products and auxiliary supplies.

Trial products must not be dispensed to any person not included in the trial. Trial product must not be used if it does not appear clear and colorless.

7.1 Trial products

Table 7–1 The following will be provided by Novo Nordisk

Trial product	Strength	Dosage form	Route of administration
Faster aspart (Fiasp [®]) (IMP)	100 U/mL	Solution for injection in vial, 10 mL	s.c.
Insulin aspart (NovoLog [®]) (IMP)	100 U/mL	Solution for injection in vial, 10 mL	s.c.

7.2 Labelling

Labelling of the trial products will be in accordance with local regulations and trial requirements. Labelling will include the product related requirements and precautions.

7.3 Storage

Table 7–2 Storage of trial products

Trial product	Storage conditions (not-in-use)	In-use conditions	In-use time*
Faster aspart (Fiasp [®])	Store in refrigerator (2°C – 8°C) Do not freeze Protect from light	Store below 30°C Do not refrigerate Do not freeze Protect from light	Use within 4 weeks
Insulin aspart (NovoLog [®])	Store in refrigerator (2°C – 8°C) Do not freeze Protect from light	Store below 30°C Do not refrigerate Do not freeze Protect from light	Use within 4 weeks

* In-use time starts when vial is removed from refrigerator (dispensing at site).

When the trial product is in the pump reservoir the in-use condition is to keep it below 37°C for a maximum of 6 days. Therefore the trial products in the pump reservoir should be discarded after no more than 6 days of use or after exposure to temperatures that exceeds 37°C.

The Investigator must ensure the availability of proper storage conditions, and also record and evaluate the temperature.

7.4 Drug accountability and destruction

Drug accountability is the responsibility of the Investigator. The Investigator or designee will perform the drug accountability at each dispensing visit and will destroy the investigational product onsite according to site SOPs.

Subjects are instructed to return all used, partly used and unused trial product at each dispensing visit, and then finally at end of treatment.

7.5 Auxiliary supplies

The Subject will use their own insulin pump, insulin infusion sets, reservoirs and sensors during the trial.

7.5.1 Auxiliaries supplied by the site

- Bayer Contour[®] Next Link meters, and strips, lancets and control solution for BG meters for subjects who do not have a personal meter
- Syringes for injection of insulin (for use with vial)

8 Randomization Procedure

At randomization (Visit 2) the Subject will be randomized to either Fiasp[®] or NovoLog[®] in a 1:1 manner at the first cross over period to the two different treatment arms described below. At the second cross over period (Visit 8) the Subject will be given the comparative treatment.

- Fiasp[®]
- NovoLog[®]

9 Adverse events, hypoglycemia, hyperglycemia, infusion site reactions, technical complaints and pregnancies

9.1 Definitions

9.1.1 Adverse events

An AE is any untoward medical occurrence in a Subject administered a product, and which does not necessarily have a causal relationship with this treatment.

An AE can therefore be any unfavorable and unintended sign (including an abnormal laboratory finding), symptom or disease temporally associated with the use of a product,

whether or not considered related to the product. AE collection will begin after the Subject signs the Informed Consent.

The current version of our local Summary of Product Characteristics (US Product Information) or any updates thereof will be used for assessment of expectedness for adverse events.

An AE includes:

- A clinically significant worsening of a concomitant illness
- A clinical laboratory AE (CLAE): a clinical laboratory abnormality which is clinically significant, i.e. an abnormality that suggests a disease and/or organ toxicity and is of a severity that requires active management. Active management includes active treatment or further investigations, for example change of medicine dose or more frequent follow-up due to the abnormality

The following should **not** be reported as AEs:

- Pre-existing conditions, including those found as a result of screening procedures (pre-existing conditions should be reported as medical history or concomitant illness)
- Pre-planned procedures unless the condition for which the procedure was planned has worsened from signing the Informed Consent
- Non-serious hypoglycemia
- Non-serious unexplained hyperglycemia

The following three definitions are used when assessing an AE:

- **Severity**
 - **Mild** - no or transient symptoms, no interference with the Subject's daily activities
 - **Moderate** - marked symptoms, moderate interference with the Subject's daily activities
 - **Severe** - considerable interference with the Subject's daily activities; unacceptable
- **Causality**

The following terms are used when assessing the relationship between an AE and the relevant trial product(s):

- **Probable** - good reason and sufficient documentation to assume a causal relationship
- **Possible** - a causal relationship is conceivable and cannot be dismissed
- **Unlikely** - the event is most likely related to etiology other than the trial product
- **Final outcome:**

- **Recovered/resolved** - the Subject has fully recovered, or by medical or surgical treatment the condition has returned to the level observed at the first trial-related activity after the Subject signed the informed consent
- **Recovering /Resolving** - the condition is still recovering/resolving at the end of the trial
- **Recovered/resolved with sequelae** - the Subject has recovered from the condition, but with lasting effect due to a disease, injury, treatment or procedure. If a sequela meets an SAE criterion, the AE must be reported as an SAE
- **Not recovered/not resolved** - the condition of the Subject has not improved and the symptoms are unchanged, or the outcome is not known
- **Fatal** - this term is only applicable if the Subject died from a condition related to the reported AE. Outcomes of other reported AEs in a Subject before he/she died should be assessed as "recovered/resolved", "recovering/resolving", "recovered/resolved with sequelae" or "not recovered/not resolved". An AE with fatal outcome must be reported as an SAE
- **Unknown** - this term is only applicable if the Subject is lost to follow-up

9.1.2 Adverse reaction

An Adverse Reaction (AR) is an Adverse Event for which the causal relationship between the Product and the Adverse Event is suspected.

9.1.3 Serious Adverse Event

An SAE is an experience that at any dose results in any of the following:

- Death
- A life-threatening experience
- In-patient hospitalization or prolongation of existing hospitalization
- A persistent or significant disability or incapacity
- A congenital anomaly or birth defect
- Important medical events that may not result in death, be life threatening or require hospitalization may be considered an SAE when - based on appropriate medical judgement they may jeopardize the Subject and may require medical or surgical intervention to prevent one of the outcomes listed in the definition of SAE
- Suspicion of transmission of infectious agents must always be considered an SAE

9.1.4 Serious Adverse Reaction

An Adverse event that will fulfill both the criteria for a Serious Adverse event and the criteria for an Adverse Reaction.

9.1.5 Non-serious adverse events

A non-serious AE is any AE which does not fulfill the definition of an SAE.

9.1.6 Hypoglycemic episodes

All plasma glucose values:

- ≤ 70 mg/dL
- > 70 mg/dL occurring in conjunction with hypoglycemic symptoms

Upon onset of a hypoglycemic episode the Subject is recommended to measure plasma glucose every 15 minutes until the SMPG value is > 70 mg/dL or symptoms have been resolved in accordance to current guidelines.

If the Subject experiences a severe hypoglycemic episode (i.e. if the subject was not able to treat themselves) the Subject should be instructed to contact the site staff as soon as possible after recovery for further guidance on titration.

9.1.7 Unexplained hyperglycemic episodes

Any unexplained hyperglycemic episode with SMPG values ≥ 300 mg/dL and no apparent explanation (i.e. no apparent medical, dietary, insulin dosage, or pump failure reason) must be recorded in the Subjects' diary. Symptoms should be treated in accordance with instructions from Investigator.

All hyperglycemic episodes that are not unexplained should be reported as AEs in accordance to section [09](#) if the Investigator judges that the hyperglycemic episode is clinically significant.

9.1.8 Infusion site reactions

If suspicion of an infusion site reaction occurs, the Subject should be instructed to call the site staff as soon as possible for further guidance.

Infusion site reactions at the site of trial product(s) administration must be recorded as an AE throughout the trial from start of screening (Visit 1) until the end of treatment visit (Visit 14).

9.2 Reporting of adverse events

The Investigator is responsible for reporting all adverse events, including SAE's to the competent authority and IRB based on federal regulations and IRB policies. All events meeting the definition of an AE must be collected and reported. This includes events from randomization until the last phone contact/site visit..

During each contact with the trial site staff, the Subject should be asked about AEs.

All AEs should be recorded by the Investigator on an AE Form. The Investigator should report the diagnosis, if available. If no diagnosis is available, the Investigator should record each sign and symptom as individual AEs using separate AE Forms.

9.2.1 Timelines for initial reporting of serious adverse events

The Investigator should complete the following within the specified timelines:

- **SAEs** - The AE Form and notification to the Novo Nordisk **within 24 hours** and to the IRB, according to the IRB guidelines. As a minimum, the following should be reported to NovoNordisk: Study name, Patient identification (e.g. subject number, initials, sex, age), Event (Preferably diagnosis), Trial drug, Reporter, Causality, Outcome.

9.2.2 Follow-up of adverse events

Follow-up information must be followed up according to the following:

- **SAEs** - All SAEs should be followed until the outcome of the event is "recovered/resolved", "recovered/resolved with sequelae" or "fatal", and until all queries have been resolved. Cases of chronic conditions, cancer or AEs ongoing at time of death (where death is due to another AE) may be closed with the outcome "recovering/resolving" or "not recovered/not resolved". Cases can be closed with the outcome of "recovering/resolving" when the Subject has completed the follow-up period and is expected by the Investigator to recover. The SAE follow-up information should only include new (e.g. corrections or additional) information and must be reported **within 24 hours** of the Investigator's first knowledge of the information. This is also the case for previously non-serious AEs which subsequently become SAEs
- **Non-serious AEs** - Non-serious AEs should be followed until the outcome of the event is "recovered/resolved" or "recovered/resolved with sequelae" or until the end of the follow-up period stated in the protocol, whichever comes first. Cases of chronic conditions, cancer or AEs ongoing at time of death (where death is due to another AE) may be closed with the outcome "recovering/resolving " or "not recovered/not resolved".

9.3 Pregnancies

9.3.1 Pregnancies in female Subjects

Female Subjects must be instructed to notify the Investigator immediately if they become pregnant during the trial until end of treatment. The Investigator must report any pregnancy in Subjects who have received trial product(s).

The Investigator should follow the pregnancy until the pregnancy outcome and the new-born infant is one month of age.

The Investigator should report information about the pregnancy, pregnancy outcome, and health of the new-born infant(s), as well as AEs in connection with the pregnancy and AEs in the fetus and new-born infant.

Investigator to report all pregnancies in trial subjects occurring during use of a Novo Nordisk Product to Novo Nordisk.

10 Quality Control Procedures

During the course of the trial, site staff will perform frequent quality checks through the duration of the study to ensure that the protocol is adhered to, that all issues have been recorded, and to monitor drug accountability. Data reviewed includes, but is not limited to, subject source charts, laboratory results, Medtronic Carelink reports, drug logs, and Subject diaries.

11 Data Handling and Record Keeping

Record keeping for this study will be handled by the Investigative site in accordance to the regulatory requirements.

Subject's data will be handled as follows:

Data already collected will be retained by the Investigator entered into the database and used for the trial report.

Safety events will be reported to Novo Nordisk and regulatory authorities according to regulatory requirements.

Data will be kept onsite at the Investigators location in a secure area through the duration of the trial and then moved offsite into a secure storage location for the required time post trial completion.

12 Statistical considerations

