6.1.9 End of treatment (Visit 14)

At end of treatment (Visit 14), the trial product should be discontinued and a stop date of trial product must be recorded in the source documentation.

The Subject should be switched to a suitable marketed product at the discretion of the Investigator and this product should be recorded on the source documentation. For procedures to be performed at end of treatment (Visit 14), please see flowchart in section [2](#).

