6.1.10 Follow-up

The follow-up period is a 30-day follow-up (Visit 15) relative to the end of treatment visit (Visit 14).

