6.1.10.1 Follow-up (Visit 15)

During the 30-day follow-up period (Visit 15) the following information will be collected:

- AEs
- Concomitant medication
- Concomitant diabetes medication
- Hypoglycemic events
- Unexplained hyperglycemic events

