6.2.4 Childbearing potential

It must be recorded in the source documentation whether female Subjects are of childbearing potential.

Female of non-childbearing potential is defined as, but not limited to:

- A female who has undergone a hysterectomy, bilateral oophorectomy, uterine ablation or bilateral tubal ligation
- Postmenopausal defined as no menses for 12 months without an alternative medical cause
- Other medical reasons preventing childbearing potential

Pregnancy testing must be performed on females with childbearing potential, as described in Section [2](#).

The Subjects must be instructed to use approved contraceptive methods, throughout the trial and until 1 week after end of treatment.

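### Pregnancies conceived late in treatment may escape notice: the subject's instruction is bounded at end of treatment, and no scheduled test or listed Visit 15 item asks about pregnancy afterwards

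*Combined protocol and SAP*

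**What the plan says.** Five provisions of the combined protocol and SAP bear on this.

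- **Subject's instruction (9.3.1).** "Female Subjects must be instructed to notify the Investigator immediately if they become pregnant during the trial until end of treatment". Under 6.1.9, end of treatment is Visit 14, the day trial product stops: "At end of treatment (Visit 14), the trial product should be discontinued".
- **Investigator's duty (9.3.1).** The investigator reports every pregnancy in a subject who has had trial product, with no end date, and follows it until the infant is one month old. A further line sends pregnancies that occur while the product is in use to its manufacturer.
- **Contraception (6.2.4).** This is required "throughout the trial and until 1 week after end of treatment".
- **Testing (flow chart in section 2, and 6.4.3).** Urine tests are scheduled at Visits 1 and 14 only. Section 6.4.3 adds unscheduled tests during the trial, for instance after a missed period, with serum confirmation of a positive result.
- **Follow-up (6.1.10, 6.1.10.1, 9.2).** Visit 15 is a phone call 30 days after Visit 14, with a window of +7 days in the flow chart. Section 6.1.10.1 opens with "During the 30-day follow-up period (Visit 15) the following information will be collected" and lists adverse events, concomitant medication, concomitant diabetes medication, hypoglycemic events and unexplained hyperglycemic events. Pregnancy is not listed. Adverse event reporting runs to the end of follow-up: "This includes events from randomization until the last phone contact/site visit".

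**The concern.** The investigator can report and follow only those pregnancies that become known. The protocol gives the investigator an open-ended duty, but the subject instruction that feeds it is bounded at the last day of treatment. The last scheduled test falls on that same day, when a recent conception may not yet show.

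The plan treats the weeks after Visit 14 as relevant for adverse events, medication and glycemic episodes, but lists nothing about pregnancy for them. At stake is whether a pregnancy exposed to trial insulin at its very start gets the outcome follow-up that 9.3.1 promises. This is a matter of safety reporting, not of the glycemic comparison.

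**Working it through.** The plan gives no figure to reproduce here. The check sets the time windows side by side and adds simple day arithmetic.

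**1. Windows counted from Visit 14 (day 0)**

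| Item | Source | Ends |
|---|---|---|
| Trial product | 6.1.9 | day 0 |
| Subject's notification instruction, narrow reading | 9.3.1 | day 0 |
| Last scheduled urine test | flow chart | day 0 |
| Contraception | 6.2.4 | day 7 |
| Follow-up call (Visit 15) | 6.1.10, flow chart | day 30 to 37 |
| Investigator's reporting duty | 9.3.1 | no end date |

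On the narrow reading, the instruction stops 7 days before contraception does and 30 to 37 days before the last contact.

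**2. Share of treatment time affected**

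Treatment lasts 2 periods × 7 weeks × 7 days = 98 days. Let d be the delay from conception until a pregnancy is detectable or noticed. The documents give no value, so I take d = 10 to 28 days as an assumption. A conception in the last d days of treatment can be missed at Visit 14. The share is d / 98:

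- d = 10: 10 / 98 = 10%
- d = 21: 21 / 98 = 21%
- d = 28: 28 / 98 = 29%

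These are shares of nominal treatment time, not probabilities of pregnancy.

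**3. Would a question at Visit 15 help?**

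The latest on-treatment conception, on day 0, becomes detectable by day d, at most day 28. That is before the earliest Visit 15 (day 30), so over the whole assumed range a question there comes late enough. A conception on day 7, the end of the contraception window, becomes detectable by day 7 + d, which is day 17 to day 35. At the upper end this can fall after a Visit 15 held on day 30. A rule that covers that week therefore also needs to admit pregnancies recognised later.

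**4. Two readings of the 9.3.1 sentence**

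- *The phrase bounds when the subject must notify.* A pregnancy recognised after Visit 14 lies outside the instruction, even if it was conceived on treatment.
- *The phrase bounds when the pregnancy begins.* A late on-treatment conception is formally covered, but no scheduled step after Visit 14 would find it.

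The notification rule differs between the readings. The lack of a scheduled step does not.

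**5. What could still reveal it**

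The missed-period test in 6.4.3 applies during the trial. Section 6.3.1 counts follow-up as part of the trial, and the stated participation of about 20 weeks fits that (2 + 14 + about 4). Section 6.2.4, however, sets a limit of one week past end of treatment in addition to the trial itself, which suggests a trial that ends sooner. So the test plausibly reaches into follow-up, but the text does not settle it, and it depends on the subject telling the site. The adverse event and medication questions at Visit 15 could reveal a pregnancy only incidentally.

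**The case against.** The strongest reply is that the 9.3.1 sentence limits when a pregnancy begins, not when the subject must speak. The last line of 9.3.1 is also framed by exposure, which supports this. A subject who conceives on treatment and learns of it three weeks after Visit 14 would then be within the instruction. This reading is at least as natural as the other, so a reader who infers that the duty definitely stops at Visit 14 goes further than the text allows.

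Three more inferences are tempting and are not supported.

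- **That all testing ends at Visit 14.** Only scheduled testing does. Section 6.4.3 plausibly carries the missed-period test into follow-up.
- **That the investigator cannot meet the reporting duty.** The duty is open-ended and nothing prevents compliance. What is missing is a dependable way of learning of the event.
- **That the extra contraception week shows missed exposed pregnancies.** Trial product has stopped by then, so a conception in that week follows exposure. Contraception that outlasts the notification instruction can simply be a safety margin.

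It is also true that the percentages rest wholly on an assumed delay, and that women of childbearing potential without adequate contraception are excluded (5.3), which makes the event less likely.

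All of this narrows the point without removing it. On either reading, nothing scheduled after Visit 14 asks about pregnancy, and the sentence that should tell subjects what to do is ambiguous.

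**Conclusion.** The point holds as a small ascertainment gap. For conceptions in about the last 10 to 28 days of treatment, 10% to 29% of the 98 days under an assumed detection delay, the plan has no scheduled step that would find the pregnancy once the Visit 14 test has passed. It relies on an unscheduled test, an incidental answer, or a subject volunteering the news under an instruction she may take to have ended.

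The documents give neither a pregnancy rate nor the number of women expected among the 40 randomised, so I put no count on it.

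Because the gap sits at the end of treatment, a reader might infer that it hides events on one insulin. It does not: section 8 randomises the order 1:1, so each insulin occupies period 2 about equally often, and a subject who withdraws in period 1 meets the same gap. The efficacy analysis, the sample size and the primary endpoint are untouched. This is worth correcting because it is cheap, not because it threatens the trial.

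**What to change.** Reconcile 6.1.10.1, 6.2.4, 6.4.3 and 9.3.1.

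1. In 9.3.1, separate the date of conception from the date of notification. For example: *female subjects are to tell the investigator, up to and including Visit 15 or whenever it is recognised later, of any pregnancy that may have begun on or before end of treatment.* The sponsor could instead bound conception by the contraception window already set in 6.2.4. That would take in a few conceptions after exposure, so the choice should be stated.
2. In 6.1.10.1 and the flow chart, add pregnancy status for women of childbearing potential to the Visit 15 items.
3. In 6.4.3, say whether the missed-period test applies through Visit 15, and use the word trial in the same sense there and in 6.2.4.

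The cost is one reworded sentence, small matching edits, and one question at a phone call already in the schedule. No visit or scheduled test is added, and the contraception requirement stays as written.
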